Days 2 through 5: effect optimization

In patients for whom the set of predetermined starting are ineffective, these days will be used to try to produce an effect on spontaneity of social interaction (eye contact, initiation of speech), observed affect, subjective mood and nervousness, and observed motivation. Adjustments initially should focus more on increasing voltage *more than* altering pulse width or frequency settings.

Exactly how many days will be involved will remain flexible, but should generally hold to the 5-day schedule as much as possible to protect the blind.

For example, a patient could come in 2 or 3 days over the course of 5, perhaps over other day. Attempts should be made to minimize the length of time patient patients who travel and require hotel rooms and need to stay for the initial optimization, ideally to one week and no more than two weeks, with visits kept roughly equivalent for active and sham patients.

Suggested configuration for the 387 lead included: 1-2- (monopolar or bipolar), 0-1-2- (monopolar or bipolar); 1-2-3- (monopolar or bipolar); 0-1-2-3- (monopolar) Frequency will be at least 135 Hz, PW at least 90 μ Sec.

Sham Optimization and Masking Procedure. Visits, ratings and other procedures will occur on the same schedule for the active and sham DBS groups from the start of Optimization until the 3-month masked DBS phase ends. The Masking Procedure described here will be identical for the active and sham patients. The only difference being that no actual parameter changes will be made for patients in the sham group as their DBS will be turned off.

During masked programming sessions the telemetry head of the DBS programming device is taped over the patient's chest. The unmasked programmer (usually the study physician) sits with the status of programming console out of the patient's view. A small cardboard shield will be affixed to the programming console to conceal whether it is turned on or off from the patient. The programmer records parameter changes (whether real or sham) and patient responses on the appropriate crf. This procedure is the same for all patients whether in the sham or the active group, with the exception of any actual programming changes for those in the sham group.

DBS Adjustment During the 3-Month Double-Masked Phase. After the optimization phase, adjustments for inadequate response (judged by the unmasked clinician) will involve adding an active cathode - either 0, 3, or potentially both, if both 1 and 2 are already active and negative. Intensity will be adjusted downwards as needed to observe the charge density limit based on measured impedance or to reduce intensity below any emergent side effects.

After the one week optimization phase, adjustments for treatment emergent adverse effects (determined by the unmasked clinician) will involve intensity reduction first, typically by 1-3V to below a detectability threshold, and, if this is insufficient, reducing the number of active cathodes by one, or changing to a different active cathode (from contact 0 to 1, e.g.) We will consider unilateral DBS, if necessary, to reduce adverse effects.

Open Continuation Phase. During open DBS, behavior therapy or medication changes will be allowed, and documented by the research team. During the open phase patients will be given a Medtronic Access Review device so that they can check stimulator battery status and DBS on or off, as an added safety measure. This device does not allow patients to change DBS amplitude, protecting against the risk of hypomania at higher currents.

Surgical Follow-up/INS Replacement. This will occur as needed, most often limited to INS replacement after battery depletion, which entails outpatient surgery under local anesthesia, expected every 10 - 24 months. All patients will be initially implanted with either the Activa PC or SC INSs. Replacement INSs may also be either Activa PCs or SCs. However, if the study psychiatrist feels they are good candidates, patients may choose to have their INSs replaced with Medtronic's Activa RC rechargeable battery and, in cases deemed appropriate by the surgeon, pocket adaptors. No Activa RC INSs will be used for initial implantation or, therefore, during the masked phase. This device requires the patient to regularly recharge the battery, thus the study psychiatrist will assess which patients will be best suited for this option. No INSs

will be replaced with Activa RCs during the blinded phase of the study.

The Activa RC offers the option of using constant current rather than constant voltage in programming. The constant current option may be used for patients receiving the Activa RC. There is the possibility that the constant current stimulus waveform might be more efficient in modulating neural activity in the circuits of interest, possibly leading to use of lower currents. If such a gain in efficiency were large enough, that in turn would lengthen recharge intervals, reducing patient burden (and conceivably extending the life of the device as well). There is also the hope that symptom relief might be better with an alternative DBS waveform using constant current stimulation. To implement this change, we would do a focused electrode survey (bilaterally). That is, contacts that were found to be active in improving symptoms will be tested in constant current mode, beginning at levels below those current levels calculated for constant voltage mode (based on measured impedance), as they are for unipolar and bipolar electrode surveys now in the protocol. We will continue to adhere to our observation routine for new parameters (observing patients after a new parameter setting) so that we can alter setting below thresholds for adverse effects (hypomania is the effect of greatest concern based on experience). As per our existing procedures, we will stay in close contact with study patients after setting changes and have them return for DBS adjustments, as we deem clinically needed. Whether long-term DBS uses constant voltage or constant current mode will be determined by clinical judgment as to which mode produces the best outcomes for a given patient. Such judgments will include YBOCS OCD severity, functional status, recharge interval, and adverse effect burden. As now, safety limits for charge density would be observed.

The Activa RC also provides additional programming options: interleaved programs and program groups. We have less specific plans for testing program groups or interleaved stimulation. If these permit stimulation regimes similar to those used before this option was available, we would like to explore these options. Again, we would use clinical endpoints to determine if these appeared beneficial in a given patient. However, it is difficult to be more specific at this stage, before we have any actual experience with the Activa RC device. It should be noted that there is the possibility that patients who have partial responses or essentially no responses might respond better to these new programming options. What we envision therefore would be a limited use of these new options during programming visits. We would consider using program sets or interleaved stimulation if an otherwise poorly- or non-responsive patient appeared to benefit.

Additional Optional Studies. Patients may choose to participate in the imaging studies performed at MGH. One study involves three FDG PET scans: at baseline, 3 months after optimization and 6 months after optimization. The other imaging study involves an O15 PET scan, which occurs after the 6-month timepoint. Both of these studies take place at MGH and are described in detail in separate consent forms approved at MGH. Patients may also choose to participate in learning task studies. One study is an Avoidance/Reward Competition task that will investigate the responses and response times during a task involving a choice to avoid or not avoid an aversive stimulus in order to receive a reward. This study will take place at MGH and is described in detail in a separate consent form approved at MGH. Participation in this task can be combined with the PET visits if the patient is participating in the imaging study, reducing the number of visits to MGH. The second learning task study is an Extinction Recall (ER) task. This task may take place at Butler Hospital particularly for Butler site patients or neuropsychological comparison group subjects who choose to participate in it. A separate Butler Hospital consent form will be used for participation in this study.

Extinction Recall Task. Using a procedure developed by our group, we will measure conditioning, extinction and extinction retention before and after three months of DBS. We hypothesize that DBS applied chronically to the VC/VS will enhance extinction recall.

We will obtain ER data on 14 patients per treatment group, for a total of 28 patients. All patients will undergo ER testing at time 0 (before surgery), and after 3 and 6 months of DBS. (Neuropsychological comparison group subject will undergo ER testing at baseline and the one-year follow-up.) The active group receives two ER tests during active DBS, after 3 months of (masked) stimulation and again at 6 months (after 6 months total of DBS). The sham group has ER testing at the same intervals: at 3 months of sham DBS, and again at 6 months (after 3 months of open-label DBS). Even though we have obtained preliminary test-retest data on healthy volunteers, which indicated the measures are stable on repeated testing, the 3-month ER test in the sham group is needed as an additional control for nonspecific effects after implantation and follow-up. The ER test after six months of continuous DBS (in the active group) will allow us to determine if the changes in fear conditioning, extinction learning, and extinction recall we hypothesize will occur during chronic DBS will be stable between 3 and 6 months. This is important to establish, since if DBS facilitates extinction, then stable changes in extinction measures should be associated with stable clinical improvement in OCD after DBS.

The protocol for fear conditioning is identical to that we developed and validated (Milad et al., 2007). Each ER test takes place on two consecutive days at 0, 3, and 6 months. The conditioned stimulus (CS+) is a visual cue, the unconditioned stimulus (UCS) is a mild shock to the fingers, and the measure of conditioned responses is the skin conductance response (SCR). The equipment consists of a “turnkey” differential aversive conditioning system (Coulbourne Instruments, Allentown, PA). In the Conditioning phase, a CS+ (e.g. blue light) is paired with the UCS and a second CS (e.g., red light) is presented during the Conditioning phase and is never paired with the UCS (CS-). The Conditioning phase will consist of a total of 5 CS+ and 5 CS- trials. The shock UCS is delivered immediately following CS+ offset with no delay between the CS+ offset and the UCS onset. After approximately 1 minute, the Extinction Learning phase will begin. During Extinction Learning, 10 CS+ and 10 CS- trials will be presented. On Day 2 (the test day), during the Recall phase, 10 CS+ and 10 CS- trials will be presented. No shocks are delivered during Recall. Contrasting CS+E vs. CS- during extinction recall allows us to assess SCR that are specific for extinction recall.

Subjects will receive \$100 per day (\$200 per two-day session) as compensation for participation. If the subjects withdraw from the study before finishing, they will receive \$20/hr for each hour they participated.

4. Data Analysis

Overall Data Management. The PI and Project Director will be responsible for and supervise data management and data. Data will be stored at in password-protected SPSS version 10 files, on a secure research server with data backup preformed nightly. Hard copies of data capture forms will be kept in locked files to which only authorized study personnel will have access. Descriptive data will be provided for all subject groups (e.g. mean age, sex, education, diagnosis, etc.). Symptom rating scales will be scored as they are in clinical use. Data Analysis will be conducted using SPSS. Data will be analyzed through analysis of variance (ANOVA), followed by appropriate post-hoc analyses.

D. Material Inducements

Symptom ratings and neuropsychological assessments will be used as they are for approved uses of DBS in movement disorders, where they are part of clinical assessment. No compensation will be offered for the measures administered in this study, except for those in the Neuropsychological Comparison Group (patients who do not undergo surgery). They will receive \$100 for the neuropsychological test sessions.

E. Training of Research Personnel

All research personnel will be trained to properly administer the study instruments by the PI and Co-PIs. All staff will receive training in responsible conduct of research based on the HHS Office of Research Integrity manual (Steneck 2004), to include data management and procedures for maintaining data confidentiality and patient safety.

III. HUMAN SUBJECTS

A. Subject Population

Participants will be patients with DSM-IV OCD of disabling severity, refractory to prolonged treatment trials with conventional medications, medication augmentation, and behavior therapy (exposure and response prevention). Inclusion and Exclusion criteria are listed above. Subjects will be patients of any race, ethnic group or gender who remain disabled with major OCD despite adequate trials of appropriate treatments. Participation or lack of it will not affect access to conventional treatments at Butler Hospital. Only subjects who are able to give fully informed voluntary written consent would be accepted. Patients who enter will be free to withdraw from the study at any time without affecting their access to other treatments at any of the above institutions. They will be at minimum 18 years old. In general, patients will continue their pre-surgical medication regimen, unless changes are viewed as medically necessary by the investigators and referring psychiatrist.

B. Recruitment and Consent Procedures

Recruitment will take place primarily via patient groups, including the Obsessive-Compulsive Foundation; and via contacts with professionals expert in OCD treatment, including presentations at national professional meetings. We will also develop a website with study information for potentially interested clinicians, patients, and families, and will list the study on ClinicalTrials.gov (now also required by many journals for publication of results). Any materials developed for the web, or other advertisements for patients, will be submitted to the IRB for approval prior to postings.

We will require that the cases of prospective patients will undergo a second process of review, by a group independent of the investigators, with expertise in OCD diagnosis and treatment and will include a patient advocacy representative. This Independent Review Group will assure that prospective patients meet the criteria above. The Group reviews written materials as to the diagnosis, severity, adequacy of previous treatment. Members of the Group will make written determinations about whether patients meet entry criteria and are able to give informed consent. If reports from all members are not received in a timely manner, the decision of the Group will be based on those reports received, provided there are at least three out of the five expected reports. The committee will review the decisions by a telephone conference, only as deemed necessary by the Group chairperson. The Group includes [name], who has personally treated more than 1000 patients with OCD and who will strive to assure that prior treatment trials have been adequate and unsuccessful, and, as patient advocate, [name], past president of the National Alliance for the Mentally Ill.

Consent for this study is a multistage process. Written informed consent for screening procedures is obtained on the first visit. Diagnostic and screening ratings are completed, followed by complete medical, neurological and neurosurgical evaluations. Case materials are presented to the Independent Review Group. If the Group agrees that study criteria are met and that the patient is appropriate for the study, consent for study treatment procedures will be obtained and the patient will enter the treatment protocol. The consent process may be videotaped with the Consent Monitor (Rev. [name]). The Consent Monitor may meet with the patient prior to the consent process and/or IRG approval to preliminarily assess their ability to provide fully informed consent. The Consent Monitor will assess whether that the patient understands the study procedures, and asks any questions they may have. The Monitor will, in addition to the study team, explain adverse effects to low literacy or non-native English speaking patients. The PET component will be discussed at the same session, with the Monitor present. It will be made clear that that PET study participation is not mandatory to receive DBS. Participants will be informed that they may discontinue their participation at anytime without penalty.

C. Potential Risks

While DBS has a generally favorable safety profile in its approved uses for movement disorders, its beneficial effects in those conditions entail potential risks. Likewise, the potential benefit of DBS for intractable OCD would not be achieved without risk. The major risks are related to surgical implantation, failure of the device, and to the stimulation itself ([name] and Rezai 2003). The informed consent language specifies the most common potential adverse effects, the most serious potential adverse events, and includes the approximate proportion of the adverse events that were due to device implantation vs. active stimulation.

Implantation Risks. Although implantation is associated with pain or discomfort for several days afterwards, its major risks are seizure, hemorrhage, and infection. In trials of DBS for movement disorders, incidence of seizure was 1% per procedure, usually controlled with anticonvulsants. The risk of intracerebral hemorrhage in the same series was 6.3%, potentially leading to neuropsychological deficits, possible paralysis, aphasia, coma, or death. The incidence of serious hemiparalysis/hemiparesis due to hemorrhage was 3.8% in that cohort. There is a 4-9% chance of infection overall, primarily involving superficial sites. In that case the brain leads would be removed and the subject treated with intravenous antibiotics. Following treatment of the infection, the procedure could be repeated.

[figure not shown]

Figure 5. DBS devices implanted

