(See Overview Figure, below). The study will use a parallel controlled design. Seven to eight patients will be implanted at Butler Hospital/Rhode Island Hospital (a total N of 30), then randomized to receive either 1) double-masked active DBS optimization followed by 3 months of masked active DBS or 2) double-masked sham optimization followed by 3 months of sham DBS. The groups will be matched for baseline YBOCS severity and gender using urn randomization. The primary outcome measure will be improvement in OCD symptoms using the YBOCS as a continuous endpoint. All patients in the sham arm will receive open DBS after three months. We will use secondary measures to determine how DBS affects symptoms which are commonly comorbid in this population (eg, depression or non-OCD anxiety), social and occupational/school functioning, and quality of life, to determine overall benefit at the three month end of masked DBS and after long-term open stimulation. Patients may choose to participate in the following additional studies: FDG PET scans, an O15 PET scan, and/or a study involving learning tasks. All of these studies are intended to illuminate the mechanisms of therapeutic effect of DBS.

To obtain an estimate of practice effects and test-retest reliability coefficients in this patient population for data analysis, we will use the same cognitive battery and testing schedule in a comparison group of OCD patients (N=24, recruited 8 per site,) who would otherwise be candidates for surgery (i.e., meet study entry criteria) but have declined this treatment option.

DBS safety will be assessed with: 1) Adverse effect questionnaires covering multiple domains, including those specific to DBS in this population as observed in our pilot work; 2) A comprehensive neuropsychological battery, including measures of personality features affected by frontobasal systems dysfunction, administered twice, at pre-surgical baseline and after 12 months of open continuation DBS; 3) Neurologic examinations at baseline and after 12 months of open DBS. The study will last for five years in order to obtain long-term effectiveness, safety and tolerability data.

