- The Stop Signal Reaction Time Task (SSRT) is a visual choice reaction time task that requires participants to respond to a target stimulus on all trials, but to try to inhibit initiated responses on trials in which a tone follows the target. In every trial, participants will see either an 'X' or an 'O' displayed on the screen. They will be instructed to respond as quickly and accurately as possible by pressing the left arrow ('X') or right arrow ('O'). In 25% of the trials a stop signal (an auditory tone) will occur at a particular stop-signal delay (SSD) after the beginning of the stimulus presentation, signaling the participant to withhold his/her response on that trial. If the SSD is short, inhibition is relatively easy. If the SSD is long, the participant's motor response will be further into execution, leaving little time to inhibit its completion. Reaction time and accuracy will be measured.
- The Self Ordered Pointing Task (SOPT) consists of 4 sets of abstract images, with three trials in each set. This task has been shown to be sensitive to DLPFC functioning. The SOPT is designed to make increasing demands on working memory: the first set has six images, the second eight images, the third set has ten images, and the last set has twelve images. The number of correct responses, the order of responses, and the time to completion of each trial will be recorded. If the participant continues to touch the same location on the page, the examiner instructs the participant that they are unable to use that particular strategy but may respond in any other way that they wish. The ratio of number of correct responses by trial to possible correct responses will be used in statistical analyses.
- Wide Range Achievement Test - Fourth Edition (WRAT-IV) - Measures academic achievement in the areas of reading, spelling, and math computation. (Wilkinson & Robertson 2006)
- NEO Personality Inventory Revised (NEO PI-R) - The NEO PI-R is a widely used self-report measure of personality. The NEO PI-R measures five personality domains including neuroticism, extroversion, openness, agreeableness and conscientiousness (Costa & McCrae 1985).
- The Obsessive Compulsive Trait Core Dimensions Questionnaire is a measure of harm avoidance and incompleteness to be completed by the participant.

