Visit and Assessment Overview (Table, above). Diagnostic and Presurgical Evaluations are done in the screening phase, involving up to 2 visits. Two to four weeks after implantation, patients have Active or Sham Optimization outpatient visits. Visits will then be monthly (at a minimum) for three months to the end of masked testing. Visits during open continuation DBS occur at Months 6, 9, 12, 18 months and then every 6 months until the study ends. To reduce subject/family burden due to travel, ratings at 9, 18, and 24 months, and every 6 months thereafter, will be via telephone. Travel reimbursement will be equitable regardless of where patients live. A trained independent rater will give all efficacy measures during the masked phase. Clinicians familiar with adverse effects of DBS in OCD patients will administer the safety and tolerability measures.

Neuropsychological Testing will be obtained at presurgical baseline, and after 12 months of open continuation DBS. Tests will be administered by a highly experienced research neuropsychologist, [name] (Butler), who will assure that administration is standardized within study patients over time.

Comparison Neuropsychological Test Group. To obtain an estimate of practice effects and test-retest reliability coefficients in this patient population for data analysis (below), we will use the same cognitive battery and testing schedule in a comparison group of OCD patients (N=24, recruited 8 per site,) who would otherwise be candidates for surgery (i.e., meet study entry criteria) but have declined this treatment option. Given the likely effects of both OCD severity and comorbid depression on the cognitive assessments, these comparison patients will be group matched for baseline YBOCS and for depression severity on the MADRS. We chose these matching variables because we thought them the most important, and balancing groups on > 2 variables is problematic. Age corrections are incorporated into the normative data for the neuropsychological measures; thus matching for age is not critical for these neuropsychological measures. Potential group IQ differences are another concern. We do not expect these based on our pilot data, which found no significant differences across the three sites. If such differences emerge in this study, we would account for them in the analysis (discussion: Data Analysis, below).

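### Age-corrected norms do not justify treating age as unimportant in a comparison group that exists to estimate retest gain

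*Protocol*

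**What the plan says.** The Study Design section and the paragraph headed Comparison Neuropsychological Test Group give the purpose of the extra group: "To obtain an estimate of practice effects and test-retest reliability coefficients in this patient population for data analysis". It is planned as "N=24, recruited 8 per site", made up of patients who would qualify for surgery "but have declined this treatment option". The battery is given twice, before surgery and after 12 months of open stimulation, and the comparison patients follow the same schedule.

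On matching, the same paragraph states that "these comparison patients will be group matched for baseline YBOCS and for depression severity on the MADRS". It explains that these two factors were thought the most important and that balancing on more than two is difficult. On age it says: "Age corrections are incorporated into the normative data for the neuropsychological measures; thus matching for age is not critical for these neuropsychological measures". For IQ it takes a different line: if group differences appear, the analysis will account for them. No such undertaking is given for age.

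In the Neuropsychological Battery section, the SOPT entry fixes the analysed variable: "The ratio of number of correct responses by trial to possible correct responses will be used in statistical analyses". The Stop Signal Reaction Time Task (SSRT) entry says only: "Reaction time and accuracy will be measured". Neither entry mentions a norm. Data Analysis (section 4) names analysis of variance with post-hoc analyses and promises descriptive data, including mean age, for all subject groups.

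**The concern.** The sentence on age argues from a premise about norms to a conclusion about matching. Two things are wrong with it.

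First, the premise addresses the wrong quantity. Age norms place one score relative to people of the same age. The comparison group is there to say how much a patient improves simply by being tested again. If norms dealt with retest gain, no comparison group would be needed. Norming the first and second scores separately does not make the difference between them independent of age.

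Second, the premise is stated for the measures without exception, while the SOPT is to be analysed as a raw proportion.

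What is at stake is the reading of cognitive change under DBS, part of the protocol's second aim. If the decliners are on average older or younger than the operated patients, and retest gain varies with age, the practice effect subtracted from the DBS group is wrong by the product of the two. A harm could be hidden or a false one suggested.

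**Working it through.** The protocol gives no power, SD or effect size for the cognitive comparison, so there is no stated figure to reproduce. The check has two parts.

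**The text**

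| Element | What the protocol fixes | Consequence |
|---|---|---|
| Purpose of the group | Practice effect and retest reliability | The target is change, not level |
| Testing | Two occasions, same schedule in both groups | A within-person change already removes any stable age effect on level, raw or normed |
| Reason for leaving age out | Norms are age-corrected | Concerns level only; says nothing about age and gain |
| SOPT | Raw ratio is the analysed variable | An explicit exception to the premise |
| SSRT | Raw outputs collected; analysed variable not fixed | A possible exception, not an established one |
| Imbalance rule | Given for IQ | None stated for age |

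It follows that bias needs two ingredients: a systematic age gap between the groups, and a slope of retest gain on age. Both raw and normed tests are exposed.

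**Illustrative size**

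Inputs from the protocol: 30 DBS patients, 24 comparison patients, ages 18 to 75. Full follow-up is assumed. Assumed, because the protocol gives neither: retest gain changes by 0.05 to 0.20 SD of the change score per decade of age, and systematic gaps of 5, 10 or 15 years.

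1. Standard error of the group difference in change, in SD units: sqrt(1/30 + 1/24) = sqrt(0.075) = 0.274.
2. Detectable difference at two-sided 5% and 80% power: (1.960 + 0.842) × 0.274 = 0.77 SD.
3. Bias = (gap in years / 10) × slope per decade.
4. False-positive rate of a nominal 5% test with no true difference: Φ(−1.96 + bias/0.274) + Φ(−1.96 − bias/0.274).

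| Systematic age gap | Bias, slope 0.05 to 0.20 | False-positive rate per measure |
|---|---|---|
| 5 years | 0.025 to 0.10 SD | 5.1% to 6.5% |
| 10 years | 0.05 to 0.20 SD | 5.4% to 11.3% |
| 15 years | 0.075 to 0.30 SD | 5.9% to 19.5% |

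For the 10-year row at the steeper slope: 0.20 / 0.274 = 0.73, and Φ(−1.23) + Φ(−2.69) = 0.109 + 0.004 = 0.113.

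**Chance gaps**

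With an assumed age SD of 12 years, two groups of these sizes drawn from the same population would differ in mean age by up to 1.96 × 12 × 0.274 = 6.4 years either way in 95% of samples. This is sampling variation. Its effect on the outcome is already inside the standard error in step 1, so it is not counted as bias here.

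**The case against.** The strongest reply is that the protocol has a second reason for not matching on age: two factors were judged the most important, and balancing more is difficult. That reason stands, and it defends the choice of matching variables. It does not show that age can be ignored in the analysis, which is the message the norms sentence gives to whoever writes the analysis plan.

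A second reply is that covariates belong in a statistical analysis plan that is not shown. That is right. The absence of an age term is not a finding; the finding is the stated rationale. Mean age by group will also be reported, so an imbalance would be visible, although nothing says what would follow from it.

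A third reply is that change scores already remove stable age effects on level, so the raw scoring of the SOPT does not by itself bias anything. This also stands. The SOPT shows that the premise is overstated; the possible harm comes from an association between age and gain.

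A reader might infer more, and the documents do not support it:

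- That several measures are analysed raw. Only the SOPT is explicit; the SSRT sentence describes data collection.
- That the bias would fall mainly on the frontal measures the protocol stresses. Many other frontal tests are listed, none of the text gives SOPT or SSRT priority, and the mechanism applies to every measure.
- That the age gap expected by chance is itself a bias of a sizeable fraction of a standard error. That would count the same variance twice.

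**Conclusion.** The point holds, at minor severity. The reason given for treating age as unimportant does not support that conclusion for a group whose task is to estimate retest gain, and its premise fails outright for the SOPT. Nothing else in the protocol repairs this: the IQ undertaking does not extend to age, and the two-variable argument concerns matching only.

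The size is unknown from the documents. They report no age distribution for either group, no evidence that decliners differ in age from those who accept surgery, and no data on how gain varies with age. A reader should not conclude that a systematic gap exists; self-selection and the wide age range make it possible. Under the assumed slopes, a 10-year systematic gap shifts the practice correction by 0.05 to 0.20 SD, against a detectable difference of about 0.77 SD. It becomes material only if the gap or the slope is large. The primary YBOCS comparison between active and sham stimulation is not affected.

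**What to change.** Remove the inference that age is not critical, or limit the statement to the level of scores on tests that have age norms. Keep group matching on YBOCS and MADRS, so recruitment is unchanged. State that age enters as a covariate in each DBS-versus-comparison analysis of cognitive change and in the estimate of the practice effect, for raw and normed measures alike.

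The cost is a few words and one degree of freedom per analysis. Age is already collected.
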